### **8.2.3 MISSING DATA HANDLING FOR PARTIAL MISSING DATES**

In general, there will be no imputation of missing dates other than for partial or missing dates where complete dates are required to flag data as treatment-emergent or concomitant with treatment. Partial/missing start and end dates for AEs and concomitant medications will be imputed as follows:

Partial/missing start date:

- Dates with missing day only will be imputed as the 1st of the month unless the month and year are same as the month and year of first dose of study medication, in which case missing day will be imputed as the first dose day of study medication.
- Dates with both day and month missing will be imputed as 1 Jan unless the year is same as the year of first dose of study medication, in which case missing day and month will be imputed as the first dose day and month of study medication.
- Completely missing dates will be imputed as the first dose date of study medication unless the end date is on or before the first dose date of study medication, in which case missing date will be imputed as 1 Jan of the same year as the end date.

Partial/missing end date:

- Dates with missing day only will be imputed as the last day of the month unless the month and year are the same as the month and year of the last dose of study medication, in which case missing day will be imputed as the last dose day of study medication.

- Dates with both day and month missing will be imputed as 31 Dec unless the year is same as the year of the last dose of study medication, in which case missing day and month will be imputed as the last dose day and month of study medication.
- If the ongoing flag is missing or “Yes” then the date will not be imputed unless death date is available, in which case the missing date will be imputed as the death date. If ongoing is “No” then the missing end date will be imputed as the last dose date.
- If the imputed date is after the date of death, then the end date will be set equal to the date of death.

The original dates will be displayed in data listings and the imputed dates will be used in derivations only (study day, treatment-emergence status, prior or concomitant medication etc).

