### **11.2 Concomitant Medications**

Prior and concomitant medications will be coded using World Health Organization Drug Dictionary (WHODrug) Global (B3, March 2020) and summarized to the therapeutic drug class (Anatomical Therapeutic Chemical [ATC] 4 classification) and preferred name. If the ATC 4 classification is not provided, the next highest classification that is provided in the coding dictionary will be used. The preferred name will be defined as the active ingredient; if the active ingredient is not provided or includes more than two ingredients (e.g., multivitamins), then the drug name will be summarized as the preferred name.

Concomitant medications are defined as those medications listed as having been taken (1) prior to initiation of study medication administration and continuing for any period of time following the first administration of study medication or (2) at any time following the first administration of study medication.

Prior and concomitant medications will be summarized using the mITT population. Medications will be tabulated for each treatment group using frequencies and percentages. Subjects may have more than 1 medication per ATC text. At each level of subject summarization, a subject will be counted once if he/she reports 1 or more medications. Percentages will be based on the number of subjects in each treatment group. In the summaries, ATC classes are listed in alphabetical order and preferred names within an ATC class are listed in order of descending frequency across all subjects.

A subject listing of prior and concomitant medications will be provided.

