### 13.1 Adverse Events

An AE is defined as any untoward medical occurrence associated with the use of a drug in humans, whether or not the event is considered drug-related. An AE can therefore be any unfavorable and unintended sign (eg, an abnormal laboratory finding), symptom, or disease occurring after the first dose of study drug, without any judgment about causality. Any pre-existing medical condition that worsens after first administration of the study drug will also be considered a new AE. The AE reporting period starts from the time the subject signs the informed consent until the subject's last study visit. All AEs will be coded using MedDRA Version 23.0.

A treatment-emergent adverse event (TEAE) is defined as any event that occurs or worsens on or after the first dose of study medication. Adverse events recorded on the eCRF which began prior to treatment and remained unchanged or improved will not be included in the summary tables but will be included in the AE data listings. For all AE summary tables, a third group other than QD and BID dose group will be presented to capture the AEs for those subjects who switched the treatment dose from QD to BID starting from Week

4. The AE that began on or after the switch will be considered treatment emergent to the BID treatment; The AE that began before the switch and continued after the switch will be considered treatment emergent to the QD treatment only; if the AE worsened on or after the switch, the new AE (one with higher severity) would become a TEAE for the BID dose and the original AE would be treatment emergent to the QD dose.

An overall summary will be presented that includes the number of events and the number and percentage of subjects who experienced at least one TEAE, by treatment group. This summary will also include breakdowns of TEAEs further categorized as ocular (study eye and fellow eye separately with TEAEs occurred on both eyes counted towards study eye once and fellow eye once) or non-ocular, TEAEs by maximum severity, TEAEs by maximum relationship to study medication, TEAE by expectedness, serious TEAEs, TEAEs leading to study medication discontinuation, TEAEs leading to death.

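### SAP 8.2.3 sets some partial start dates to the first-dose date without checking the end date, so an adverse event that ended before treatment can be flagged as treatment-emergent

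*SAP*

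**What the plan says.** SAP 8.2.3 gives three rules for an incomplete start date of an AE or medication:

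- **Day missing.** Use the 1st of the month, except when month and year are those of first dose, "in which case missing day will be imputed as the first dose day of study medication".
- **Day and month missing.** Use 1 January, except when the year is that of first dose, "in which case missing day and month will be imputed as the first dose day and month of study medication".
- **Completely missing.** Use the first-dose date, "unless the end date is on or before the first dose date of study medication"; the fallback is then 1 January of the end-date year.

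The same section says that "the imputed dates will be used in derivations only (study day, treatment-emergence status, prior or concomitant medication etc"), while listings show the original dates.

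SAP 13.1 defines a treatment-emergent AE (TEAE) as "any event that occurs or worsens on or after the first dose of study medication". It also says that recorded AEs "which began prior to treatment and remained unchanged or improved will not be included in the summary tables", and are only listed. SAP 11.2 counts a medication as concomitant if it was taken before first dose and continued, or under limb "2) at any time following the first administration of study medication".

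**The concern.** The third rule shows that the authors foresaw a record whose end date places it before treatment, and protected against it. The first two rules lack that protection. No later rule in SAP 8.2.3 caps an imputed start at the end date; the only cap concerns end dates and death.

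The affected records are those with a partial start in the first-dose month or year and a recorded end before first dose. Their timing relative to treatment is known, because the end date settles it. The rule replaces that knowledge with a start on Day 1. The result is an impossible pair of dates in the analysis dataset and, for AEs, an event charged to netarsudil that was over before the first drop.

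Such records can arise. SAP 13.1 states that "The AE reporting period starts from the time the subject signs the informed consent", Protocol 6.9.1 asks for events in the washout period to be recorded as AEs, and Protocol 6.3 collects medications from 30 days before screening. Safety is a secondary objective, and in arms of up to 20 subjects a single misclassified event is visible in a table.

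**Working it through.** The documents state no figure for this rule, so there is none to reproduce. The check applies the three rules literally to example records.

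**Inputs**

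- The three start-date rules: SAP 8.2.3.
- TEAE if the start is on or after first dose: SAP 13.1. Protocol 9.8.7 says after first dose, but SAP Section 1 states that the SAP's methods supersede the protocol's.
- First-dose date taken as the first dispensation date: SAP 3.1 and 8.3.
- Up to 20 subjects per group and 40 in total: SAP Section 5.
- First dose on 20 April 2021: an assumption, for illustration only.

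**Results**

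| Record | Start under the SAP | Flag under the SAP | Start with end-date check | Flag with check |
|---|---|---|---|---|
| AE, start April 2021 (day unknown), end 17 April | 20 April, 3 days after its end | TEAE | 1 April | not TEAE |
| AE, start 2021 (day and month unknown), end 17 April | 20 April, 3 days after its end | TEAE | 1 January | not TEAE |
| Same AE, start completely missing, end 17 April | 1 January | not TEAE | 1 January | not TEAE |
| AE, start April 2021 (day unknown), end 25 April | 20 April | TEAE | 20 April | TEAE |
| Drug, start 2021 (day and month unknown), end 18 April | 20 April, 2 days after its end | concomitant by start date | 1 January | not concomitant |

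The first three rows show the anomaly. The record with no start date is classified correctly, and the same event with a known month or year is not. The fourth row shows that the check leaves a truly ambiguous event treatment-emergent.

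**Does the impossible date always follow?** Take a 30-day month, every possible first-dose day d, a start known to the month only, and an end 1 to 8 days before first dose within that month. The number of pairs is the sum over d of min(d − 1, 8):

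- d = 1 to 9: 0 + 1 + … + 8 = 36
- d = 10 to 30: 21 × 8 = 168
- total: 36 + 168 = 204

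Under the SAP rule the imputed start falls after the recorded end in 204 of 204 pairs; with the check, in 0 of 204. These are all records of the affected type, so the count shows that the error is systematic for that type. It says nothing about how often such records occur. None of the examples or pairs ends on the first-dose date itself, so the results are the same whether the check is written as before or as on or before first dose.

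**Size of one misclassified subject:** 1/20 = 5.0 percentage points of an arm, and 1/40 = 2.5 points of both arms combined.

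**The case against.** The strongest defence is the opening of SAP 8.2.3, which allows imputation only where a complete date is needed to set the treatment-emergent or concomitant flag. If the end date precedes first dose, no start date is needed, so such records would never reach the rules. The third rule undercuts this reading: it imputes a date for exactly such records and guards against the error. A programmer might skip them, but the text does not say to.

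The default to first dose is also a reasonable conservative choice when the end date is unknown. That stands; the point concerns only records with a recorded end.

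Exposure for AEs is small, and this stands too. The event must begin after consent and end before Day 1, and Screening is Day -8 to -1. Conditions already present at screening go to medical history (Protocol 6.2), AEs are source verified (Protocol 10.6), and data omissions and discrepancies are queried (Protocol 10.11).

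For drugs, a reader might infer that hypertonic saline or carbonic anhydrase inhibitor drops stopped in washout (Protocol 5.6.1) would be reported as prohibited drugs taken on treatment. The documents do not support that:

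- SAP 11.2 turns on when the drug was taken, so a program that also tests the recorded end date would not flag it, although the impossible start would remain.
- Tables 14.1.4.1 and 14.1.4.2 pool prior and concomitant medications, so their counts would not change.
- Prohibited use is reviewed as a protocol deviation (SAP Section 9), with final classification by the sponsor (SAP 6.1). Nothing says that imputed dates feed that review.

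**Conclusion.** The point holds, as a minor one. Applied as written, the first two start-date rules give a start after the recorded end, and a false TEAE, for any AE with a partial start in the first-dose month or year and a recorded end before first dose. This conflicts with the stated intent of SAP 13.1. For drugs the consequence is conditional: the concomitant flag is wrong only if it is derived from the imputed start alone.

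The 5 percentage points are an upper limit per event in an arm of 20. SAP 13.1 counts a subject once per preferred term and once per organ class, so a subject with another qualifying TEAE in that row adds nothing. The number of affected records cannot be told from the documents; for AEs it is likely to be few. The primary analysis of central corneal thickness does not use these dates and is unaffected.

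The conclusion assumes that the rules are programmed literally and that the end date is recorded.

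**What to change.** Add to the day-missing rule and to the day-and-month-missing rule the exception that the third rule already has, with the same boundary: if the end date is on or before the first-dose date, impute the 1st of the known month or 1 January of the known year, respectively. An event recorded as ending on the first-dose date then falls back as well, as it already does under the third rule, and the section keeps a single threshold. State also that an imputed start date may not be later than the recorded end date.

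The end-date rules need no change for this point. The cost is a sentence or two in SAP 8.2.3 and a small change to the date derivation. No new data are needed.

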### 8.3 Definition of Baseline

Baseline is defined as the last measurement (including measurement from unscheduled visits) prior to the first dose of study medication. The date of first dose of study medication is assumed to be same as the first study medication dispensation date.

### 8.4 Data Analysis Conventions

All data analysis will be performed by SDC. Statistical programming and analyses will be performed using SAS® Version 9.4 or higher. Output will be provided in rich text format (RTF) for tables and portable document format (PDF) for tables, and listings using landscape orientation. Unless otherwise specified, all study data for randomized subjects will be listed by treatment group, subject number, visit, and parameter as applicable. Only a disposition listing will be created for screen failure subjects. Summaries will be presented by treatment group and visit as applicable.

Continuous study assessments will be summarized by treatment group and visit as applicable using descriptive statistics (n, mean, median, SD, minimum, and maximum). Minima and maxima will be reported with the same precision as the raw values; means and medians will be presented to one additional decimal place than reported in the raw values. Standard deviations will be presented to two additional decimal places than reported in the raw values. Categorical study assessments will be summarized by treatment group and visit as applicable using discrete descriptive statistics (frequency counts and percentages). All percentages will be rounded to one decimal place (ie, XX.X%). Change from baseline will be calculated as follow-up visit – baseline visit.

Hypothesis testing, unless otherwise indicated, will be performed at a 2-sided with a significant level of 0.10 ( $\alpha = 0.1$ ). Where applicable, 2-sided 90% and 95% confidence intervals (CIs) will be reported. All p-values will be displayed to four decimal places, with p-values less than 0.0001 presented as "<0.0001" and p-values greater than 0.9999 presented as ">0.9999". All odds ratios less than 0.01 will be presented as "<0.01" and all odds ratio greater than 999.99 will be presented as ">999.99". Difference between netarsudil QD and netarsudil BID will be calculated as netarsudil QD – netarsudil BID.

## 8.5 Adjustments for Multiplicity

Adjustments for multiplicity will not be made in this early phase trial.

## 9. Disposition of Subjects

Disposition will be presented in terms of numbers and percentage of subjects by treatment group and for all subjects. Percentages will be calculated using treated subjects as the denominator unless otherwise specified.

The numbers and percentages of subjects who were screened, enrolled, screen failed, and treated will be presented. The reasons for screen failure will be displayed with the percentages calculated using total number of screen failures as the denominator. The screen failure reason will include eligibility criteria not met, lost to follow up, investigator decision, enrollment complete, withdrawal of consent, and other. The number of subjects with COVID-19 related screen failure will be identified.

The number and percentages of subjects in each analysis population (mITT, PP, and Safety) will be presented.

The number and percentage of subjects who completed the study or prematurely discontinued from the study will be presented. The reasons for study discontinuation will include AE, withdrawal of consent, non-compliant, lost to follow up, lack of efficacy, disallowed concurrent medication, investigator decision, protocol deviation, and other. Percentages will be calculated using the number of discontinued subjects as the denominator. The number of subjects with COVID-19 related study discontinuation will be identified.

The number and percentage of subjects with any deviation, major deviation, and minor deviation will be presented. The protocol deviations that will be reviewed include informed consent, inclusion/exclusion, test article/study drug instillation and assignment at site, improper protocol procedures at site, site's failure to report serious adverse event (SAE)/AE, visit out of window, subjects' use of prohibited concomitant medication, subjects' failure to follow instructions and other. The number of subjects with COVID-19 related protocol deviations will be identified.

In addition, subject listings for randomization schedule, disposition (for all randomized subjects and for screen failed subjects), protocol deviations, COVID-19 related protocol deviations, and analysis populations will be provided.

## 10. Demographic and Pretreatment Variables

### 10.1 Demographic Variables

The demographic variables including age, sex, race, and ethnicity will be summarized for mITT population.

Age (years) will be summarized by treatment group and for all subjects, using continuous descriptive statistics. In addition, age will be categorized into four age groups, <18, 18–65, 66–75, >75, and summarized using counts and percentages.

Sex, race, and ethnicity will be summarized by treatment group and for all subjects using discrete descriptive statistics. Subjects who record more than one race will be grouped into a single category denoted as multi-racial.

Subject listings will be provided for demographic variables, childbearing potential for female subjects, and pregnancy tests for female subjects with childbearing potential.

## **11. Medical History and Concomitant Medications**

### **11.1 Medical History**

Medical and ophthalmic history will be obtained at the Screening and Baseline visit and coded using Medical Dictionary for Regulatory Activities (MedDRA) Version 23.0.

Medical history will be summarized using discrete descriptive statistics and presented by treatment group and for all subjects at the subject level by System Organ Class (SOC) and Preferred Term (PT) using the mITT population. Ocular and non-ocular medical history will be summarized separately. If a subject reports the same PT multiple times within the same SOC, that PT will only be reported once within that SOC. If a subject reports multiple conditions within the same SOC, that SOC will only be reported once. In the summaries, SOCs are listed in alphabetical order; PTs within a SOC are listed in order of descending frequency across all subjects.

Subject listings will be provided for ocular medical history, ocular surgery and laser procedure, and non-ocular medical history.

### **11.2 Concomitant Medications**

Prior and concomitant medications will be coded using World Health Organization Drug Dictionary (WHODrug) Global (B3, March 2020) and summarized to the therapeutic drug class (Anatomical Therapeutic Chemical [ATC] 4 classification) and preferred name. If the ATC 4 classification is not provided, the next highest classification that is provided in the coding dictionary will be used. The preferred name will be defined as the active ingredient; if the active ingredient is not provided or includes more than two ingredients (e.g., multivitamins), then the drug name will be summarized as the preferred name.

Concomitant medications are defined as those medications listed as having been taken (1) prior to initiation of study medication administration and continuing for any period of time following the first administration of study medication or (2) at any time following the first administration of study medication.

Prior and concomitant medications will be summarized using the mITT population. Medications will be tabulated for each treatment group using frequencies and percentages. Subjects may have more than 1 medication per ATC text. At each level of subject summarization, a subject will be counted once if he/she reports 1 or more medications. Percentages will be based on the number of subjects in each treatment group. In the summaries, ATC classes are listed in alphabetical order and preferred names within an ATC class are listed in order of descending frequency across all subjects.

A subject listing of prior and concomitant medications will be provided.

## 12. Efficacy Analyses

Efficacy assessments include CCT by ultrasound pachymetry, BCVA using Early Treatment of Diabetic Retinopathy Study (ETDRS) method, tomography (Pentacam®) and V-FUCHS questionnaire that are described in Section 12.1. All collected efficacy measurements will be presented in subject listings. Efficacy analyses for primary, secondary, and exploratory endpoints will be produced in summary tables as specified in Sections 12.2, 12.3, and 12.4.

### 12.1 Efficacy Assessments

#### 12.1.1 CENTRAL CORNEAL THICKNESS BY ULTRASOUND PACHYMETRY

CCT will be measured at all scheduled visits for both eyes at approximately the same time of day  $\pm$  60 minutes, always before noon (local time) and always performed before IOP measurements. Every effort should be made to ensure that the same individual performs the measurement and uses the same device for a given subject at each visit. Five consecutive measurements of CCT will be measured for each subject, for each eye at each visit. The mean CCT and SD of the five readings will be recorded, and the mean will be analyzed for efficacy.

#### 12.1.2 BEST CORRECTED VISUAL ACUITY BY ETDRS METHOD

The BCVA assessment using the ETDRS method will be performed at all scheduled visits for both eyes following manifest refraction, and prior to the slit lamp examination. BCVA will be analyzed for efficacy and presented as letter score and logarithm of the minimum angle of resolution (logMAR), calculated as:  $(85 - \text{letter core})/50$ .

